7.5 DETERMINATION OF SAMPLE SIZE

As mentioned before this is a hypothesis generating trial. No primary hypothesis or primary endpoint have been formulated. Approximately 600 patients are planned to be randomized with 400 receiving PhI therapy and 200 PPCI. A minimum of approximately 100 patients \geq 70 years of age will be randomized to the PhI arm. The aim is to combine ECG and angiographic data from the latter group with similar data from STREAM-1^{16, 18} in order to have a more reliable estimate of the efficacy of the PhI strategy in elderly patients. The analysis of ECG data, angiographic data and clinical events will be described in detail in the statistical analysis plan. Although the study of 600 patients is not powered to show a difference in clinical events, given the elderly nature of the population there will be ample efficacy and safety events to observe. They will be reported along with their 95% confidence limits. For reference, in patients \geq 60 years from STREAM-1 the 30 day composite of death, shock, heart failure and re-MI ranged between 18 and 20 % for PhI and PPCI groups. Bleeding data in this age group were 1.7 % and 0 % ICH and 8.8 % and 7 % non-intracranial major bleeding respectively. If the study would turn into a confirmatory trial after the interim analysis a primary hypothesis on a combined clinical endpoint will be pre-specified.

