## **5 Handling of Missing Data**

Best efforts will be made to collect complete data for the clinical endpoints of interest, regardless of whether or not the subject received study drug/treatment. In order to minimize bias and take all randomised patients into the analysis when the proportion of missing data for a specific endpoint is larger than 1%, a multiple imputation analysis will be performed. Only endpoints listed in Sections 6.1 to 6.4, with the exception of the ECG endpoint Sum ST-segment deviation

resolution 30-min post-angiogram/PCI, will be imputed, if necessary. No imputation for the endpoints listed in Section 6.5 will be performed.

The baseline covariates age, sex, assigned treatment, body weight, infarct location (anterior or other), previous infarction, Killip class, heart rate, systolic blood pressure and time from symptom onset to randomisation, hypertension, diabetes, place of randomization, Q-wave, time of randomization (before or after protocol amendment 5), time of randomization to administration of tenecteplase or sheath insertion and type of access together with all single efficacy and safety endpoints, ECG (with the exception of the endpoint Sum ST-segment deviation resolution 30-min post-angiogram/PCI) and angiographic endpoints will be multiply imputed using the fully conditional specification (FCS) method using a regression or logistic regression model, whichever is applicable. Note that for the ECG endpoint successful reperfusion, the imputation will be done on the ST-segment resolution from which successful reperfusion will be determined. For mortality, the variables cardiac and non-cardiac mortality instead of overall mortality will be used. For non-intracranial bleeds, only the variables major and minor non-intracranial bleeds will be put in the model. Total non-intracranial bleeds will be determined later on. For stroke, the variables total stroke, will be put in the model. The subclassifications of ischaemic, intracranial haemorrhage, fatal, non-fatal, disabling, non-disabling will be done in a second phase in which the type will be imputed by a random draw from a binary distribution with a probability of success equal to the maximum of the observed event rate or 0.01 stratified by assigned treatment

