Before the large imputation will take place, the following procedure will be applied. In case it is known that a patient died, but the cause is unknown, cardiac or non-cardiac mortality will be first determined by imputing the cause by a random draw from a binary distribution with a probability of success equal to the maximum of the observed event rate or 0.01 stratified by assigned treatment.

The value 12345 will be used as seed for all the imputations. In case of computational problems for the large imputation model, primarily 5 times different seed values will be used augmenting the seed number by 1 (12345 to 12349). If computational problems persist, the endpoint with the fewest number of overall events is deleted from the imputation scheme and handled separately later on. In case there are several variables with the same small number of

events, the variable which comes first in the alphabetical order will be omitted first. The same procedure with at most 5 random seeds is tried again with one variable less in the imputation scheme. This process is iterated until a successful multiple imputation has been obtained. The endpoint(s) that has (have) been omitted from the imputation scheme will be imputed by a random draw from a binary distribution with a probability of success equal to the maximum of the observed event rate or 0.0001 stratified by assigned treatment. Combined endpoints will be constructed based on the imputed single endpoints. A total of 100 imputations will be performed. The default number of burn-in iterations will be applied.

For all other endpoints, best efforts will be made to collect complete data for the events of interest. All percentages will be calculated on the number of subjects with non-missing information.

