#### **6.1.2 ECG-based endpoints**

- Successful reperfusion: (Worse-lead ST-segment elevation resolution  $\geq 50\%$  30-min post-angiogram/PCI)
- Sum ST-segment deviation resolution 30-min post-angiogram/PCI

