## **8.5.2 ECG based endpoints**

### **8.5.2.1 Successful reperfusion 30 minutes after angiogram/PCI**

Successful reperfusion will be analysed using a relative risk for treatment effect as described in Section 8.5.1.

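### Imputing ST-segment resolution by regression and then cutting it at 50% can bias the successful-reperfusion rate, in a direction the documents do not settle; predictive mean matching is a cheap improvement

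*SAP*

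**What the plan says.** SAP Section 5 starts multiple imputation on a low trigger: "when the proportion of missing data for a specific endpoint is larger than 1%, a multiple imputation analysis will be performed". Baseline covariates, single clinical endpoints, and ECG and angiographic endpoints enter one model, "using the fully conditional specification (FCS) method using a regression or logistic regression model, whichever is applicable". For the ECG responder endpoint it adds that "the imputation will be done on the ST-segment resolution from which successful reperfusion will be determined". SAP 6.1.2 lists that endpoint among those of primary interest ("Successful reperfusion: (Worse-lead ST-segment elevation resolution" of at least 50%, 30 minutes after the procedure), and SAP 8.5.2.1 gives the analysis: "Successful reperfusion will be analysed using a relative risk for treatment effect as described in Section 8.5.1".

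No transformation, bound or matching step is named for ST-segment resolution. The companion variable, sum ST-deviation resolution, is left out of the imputation and is summarised in SAP 8.5.2.2 by median and quartiles with a rank test. SAP 6.2 adds a 60-90 minute version of successful reperfusion in Group A only. Section 5 puts the endpoints of Sections 6.1 to 6.4 in scope for imputation, so this version appears to be covered too.

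Protocol 7.3 foresees no imputation at all. That difference is a separate matter.

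**The concern.** For a continuous variable, regression in an FCS scheme is naturally read as a linear model with normally distributed residuals, although the SAP does not use the word normal. Percent resolution of ST elevation has a ceiling at 100% by definition. It can also be negative if elevation worsens, so a skewed distribution is plausible.

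When the imputed value is afterwards dichotomised, what counts is the share of imputed draws on each side of 50%. A normal curve with the right mean and variance need not reproduce that share. At stake is the accuracy of a responder rate that is an endpoint of primary interest, is reused in the subgroup analyses (SAP 8.11) and is carried into the pooled elderly sets (SAP 9.1.2.1). If post-procedure ECGs are missing more often in one arm, the error does not cancel in the relative risk.

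**Working it through.** **Inputs from the documents.** The cut is 50% and the ceiling is 100%. Protocol 7.5 gives the size: "Approximately 600 patients are planned to be randomized with 400 receiving PhI therapy and 200 PPCI". SAP Section 5: "A total of 100 imputations will be performed". The documents give no distribution, no missing rate and no success rate at 30 minutes after the procedure, so there is no stated figure to reproduce. The nearest anchor is Protocol 5.3.3, which expects rescue in 25-30% of lysed patients. That implies about 70-75% with adequate resolution at 90 minutes, a different time point.

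**Assumptions.** True success of 70-95%, the shapes below, and 2-20% missing.

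**Step 1: bias among imputed patients, by hand.** Let resolution be 100(1 − R), with R exponential with mean θ (left-skewed, capped at 100, worsening possible). True success is p = 1 − exp(−0.5/θ), so θ = 0.5/(−ln(1 − p)). A normal distribution with the same mean and SD gives success Φ((0.5 − θ)/θ) = Φ(−ln(1 − p) − 1).

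| True p | Mean, SD | Normal gives | Bias (points) |
|---|---|---|---|
| 70% | 58.5, 41.5 | Φ(0.204) = 58.1% | −11.9 |
| 75% | 63.9, 36.1 | Φ(0.386) = 65.0% | −10.0 |
| 80% | 68.9, 31.1 | Φ(0.609) = 72.9% | −7.1 |
| 85% | 73.6, 26.4 | Φ(0.897) = 81.5% | −3.5 |
| 90% | 78.3, 21.7 | Φ(1.303) = 90.4% | +0.4 |
| 95% | 83.3, 16.7 | Φ(1.996) = 97.7% | +2.7 |

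Other left-skewed shapes (R gamma or lognormal, with 0-40% of patients exactly at 100%) gave −0.5 to −17.5 points at 70%, +0.6 to −15.3 at 80%, +1.7 to −5.9 at 90% and +0.7 to +3.0 at 95%.

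For a beta distribution on 0-100, also left-skewed but with no worsening, the sign reverses. With Beta(a, 1) and p = 80%, a = ln 5/ln 2 = 2.32, mean 69.9, SD 22.1, and Φ(0.902) = 81.6%, a bias of +1.6 points. Across beta shapes the range was +1.4 to +1.9 at 80% and +2.4 to +3.8 at 90%.

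**Step 2: bias in the arm rate.** When missingness is unrelated to outcome, this is the Step 1 bias times the missing fraction. A bias of −10 points becomes −0.2 at 2% missing, −0.5 at 5%, −1.0 at 10% and −2.0 at 20%. Even −17.5 points gives −0.9 at 5%.

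**Step 3: simulation** (400/200 patients, arm and one covariate in the model, 20 imputations; the number does not affect bias). Missingness depends on the covariate, except in the 15%/5% row, where it is completely at random. PMM is predictive mean matching with 5 donors.

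| Setting (PhI/PPCI) | Full data | Regression | PMM |
|---|---|---|---|
| 80/75% success, 10% missing | 80.0/75.1 | 78.7/73.6 | 80.0/75.0 |
| 80/75% success, 20% missing | 80.0/74.5 | 77.6/71.9 | 80.0/74.5 |
| 95/92% success, 10% missing | 94.9/91.9 | 95.2/92.5 | 94.9/92.0 |
| 75/75% success, 15%/5% missing | 74.9/74.9 | 72.8/74.1 | 74.9/74.8 |

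With missingness set at 10% but strongly dependent on the covariate, regression was low by about 2 points in each arm (77.9/73.2 against 79.9/75.0).

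**Step 4: relative risk.** Equal missingness: 1.070 by regression against 1.066 in full data at 10%, and 1.079 against 1.074 at 20%. Unequal missingness: at 20% v 10%, 1.053 against 1.070; at 15% v 5% with a true value of 1.00, 0.983 against 1.001. The Step 1 exponential shape gives the same order for 15% v 5%: (75 − 0.15 × 10.0)/(75 − 0.05 × 10.0) = 73.5/74.5 = 0.987. A separate run with another shape gave 0.992 against 1.000. Interval coverage for regression stayed at 93-98%.

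**Step 5: limits of matching.** With arms of different shape sharing donors and 20% missing, PMM was off by −0.3/+0.5 points, against −2.5/−1.7 for regression. In small sets (75/40 patients) with strongly covariate-dependent missingness it was off by about +0.4/+0.6, against −1.8/−1.6.

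**The case against.** The strongest reply is that the step hardly matters. Regression imputation is standard. The trial is hypothesis-generating with no primary endpoint. At 85% success the standard error of the difference in rates is √(0.85 × 0.15 × (1/400 + 1/200)) = 3.1 points, well above any bias expected at low missingness. With equal missingness the relative risk barely moves. This stands, and it limits the point to a small improvement.

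A reader might also infer that the plan understates successful reperfusion. The documents do not support that as a general statement. The sign depends on where 50% falls in a distribution they do not describe and on a 30-minute success rate they do not give; the 90-minute anchor precedes PCI in most patients.

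It is also tempting to cite impossible draws: under the exponential shape a normal puts Φ(−1) = 16% above 100%. At this cut that shows the model is a poor description, not that it does harm, because a draw of 110% and one of 95% both count as success.

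What the reply does not meet is that an unknown sign is no argument for keeping the method when an alternative follows the observed distribution.

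**Conclusion.** The point holds as a cheap improvement of small size. Section 5 can bias the imputed successful-reperfusion rate, in a direction that cannot be fixed from the documents. Under the assumed shapes the arm-level bias is typically below 1 point at up to 5% missing and roughly 0 to 1.5 points at 10%, reaching about 2 points at 10% only when missingness depended strongly on a covariate.

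A reader might infer that the treatment comparison is biased. That needs missingness to differ by arm, and the documents give no evidence either way. In the runs with 15% v 5% missing, a true relative risk of 1.00 came out at 0.983 to 0.992.

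The conclusion rests on reading regression as linear with normal residuals and on assumed shapes, success rates and missing rates. It concerns ST-segment resolution only; nothing here was shown for other continuous variables in the model.

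**What to change.** In SAP Section 5, name FCS predictive mean matching as the method for worst-lead ST-segment resolution at 30 minutes after the procedure and, where it is imputed, at 60-90 minutes after tenecteplase. State the number of donors, and preferably match within arm. Keep logistic models for the binary endpoints. Report the number of missing ECGs by arm beside the endpoint. Optionally, add a sensitivity analysis that imputes the binary endpoint directly by logistic regression.

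The cost is a short text change and a different method option in the imputation procedure; no new data are needed. It is not entirely free. A donor number has to be chosen, and small residual bias is possible where donors are few, as in the pooled elderly sets. If matching within arm is done by running the whole imputation separately by arm, the rare binary endpoints have fewer events per model. The SAP should therefore say whether the split applies to the whole model.

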## **6 Endpoints**

### ***6.1 Efficacy endpoints of primary interest***

#### **6.1.1 Clinical endpoint**

The efficacy endpoint of primary interest is all cause death, shock ,CHF and reinfarction at day 30.

#### **6.1.2 ECG-based endpoints**

- Successful reperfusion: (Worse-lead ST-segment elevation resolution  $\geq 50\%$  30-min post-angiogram/PCI)
- Sum ST-segment deviation resolution 30-min post-angiogram/PCI

#### **6.1.3 Combined ECG and clinical endpoints**

- Incidence of aborted myocardial infarction (in both groups)
- Need for rescue PCI/revascularization as determined by investigator in Group A.

- Need for rescue PCI/revascularization as determined by central adjudication in Group A

#### **6.1.4 Angiographic endpoints**

- TIMI flow at first and last coronary angiography (as reported by investigator)

### **6.2 Efficacy Secondary Endpoints**

The following observations are considered as endpoints evaluating the efficacy and will be assessed at day 30. They are ordered according to medical importance in the indication acute myocardial infarction.

- All cause mortality
- Cardiac mortality
- Cardiogenic shock
- Congestive heart failure (CHF)
- Recurrent myocardial infarction (reinfarction)
- All cause death and shock
- All cause death and shock and reinfarction
- All cause death and shock and CHF
- Rehospitalization for cardiac reasons
- Rehospitalization for non-cardiac reasons

In addition, successful reperfusion (worst-lead ST-segment elevation resolution  $\geq 50\%$  60-90 min after injection of tenecteplase) will be reported in group A only: overall and by adjudicated rescue status.

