4.1.4.2 Group PPCI

Pre-PCI hospital (ambulance/ER community hospital) treatment:

Acetylsalicylic acid

Acetylsalicylic acid is expected to be administered routinely to all patients at a dose of 150-325 mg p.o. Alternatively, if the patient is unable to ingest tablets, the initial dose may be given intravenously (80 to 150 mg i.v.). If a patient has already taken acetylsalicylic acid within 12 hours prior to screening the patient will start with acetylsalicylic acid the next day (maintenance dose: 75 to 100 mg).

P2Y12 antagonist

A P2Y12 antagonist is to be administered according to local practice and international guidelines. Prasugrel should not be administered to any patient \geq 75 years of age. cfr FDA product label.

Antithrombin treatment according to local standards and in accordance with international PCI guidelines (e.g., unfractionated heparin/ enoxaparin/ bivalirudin).

In-PCI hospital treatment:

At the receiving PCI hospital transfer to the catheterisation laboratory should be organised as soon as possible as per local practice and in accordance with the protocol timelines. The patient should be admitted preferably directly to the catheterisation laboratory.

Standard PPCI

Standard PPCI procedure following angiography (use of additional GP IIb/IIIa antagonists is at the investigator's discretion). As per current guidelines, only PCI of the infarct related vessel should be performed. PCI of non-infarct related vessels is NOT recommended. For details please refer to section 6.2.2.2.

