6.2.3 End of trial and follow-up period

6.2.3.1 End of trial (day 30)

The end-of-trial visit will take place at day 30. Data may however be collected until and including day 37. If a visit at the outpatient clinic is not possible the patients may be contacted by phone. The following data will be collected:

- Data on any rehospitalisation occurring after hospital discharge up to (including) day 30
- Any occurrence of adverse events, and serious adverse events/serious clinical events since hospital discharge or (if the patient is still hospitalised) that have not yet been recorded

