Aborted myocardial infarction⁵⁴ will be assessed by means of ECG as ST-segment resolution relative to baseline value and cardiac marker enzymes as done previously in STREAM-1⁵⁵. Peak levels of troponin I/T (CK/CK-MB) will be collected at baseline, and 8-12 hrs and 24 hrs after randomisation. Quantification of aborted myocardial infarction will be defined as troponin values \leq 5 times the upper limit of normal (ULN) within 24 hours of randomisation (or CK/CK-MB levels \leq 2 times ULN). Only peak values of markers of necrosis (expressed as times exceeding the upper limit of normal) will be recorded in the eCRF; the complete set of measured values will however be kept in the source documents.

Rescue PCI post PPI therapy

If ST-segment resolution is $<50\%$ relative to the ST-segment elevation in the qualifying lead at baseline, irrespective of the presence or absence or clinical symptoms

Refractory ischaemia

Symptoms of ischaemia with ST-deviation or definite T-wave inversion persisting for at least 10 min despite medical management while in-hospital and not fulfilling the diagnosis of infarction.

Major arrhythmias

Sustained ventricular tachycardia (ventricular tachycardia lasting ≥ 30 seconds or requiring cardioversion or causing symptoms/hypotension), ventricular fibrillation, asystole, atrial fibrillation, 2nd and 3rd degree atrio-ventricular block.

Invasive procedures

Include CABG, PTCA, stent placement, intra-aortic balloon.

Other major cardiac events

Other major cardiac events include sustained hypotension, acute mitral regurgitation, acute ventricular septum defect, pericarditis, pulmonary embolism and tamponade.

Sustained hypotension

SBP < 90 mmHg for > 30 minutes

Rehospitalisation for cardiac reasons

If, after discharge, a patient is readmitted to the hospital until day 30 due to cardiac reasons, this information must be recorded in the eCRF. Any event requiring unscheduled readmission will be considered a serious adverse event (SAE) and recorded as described in section 5.2.1. Only if readmission was scheduled, e.g. because of a routine or planned procedure, will the event leading to rehospitalisation not be considered as a serious adverse event.

Rehospitalisation for non-cardiac reasons

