#### **6.6 Additional in-hospital events**

- Serious major arrhythmias (defined as AV block, atrial fibrillation, sustained ventricular tachycardia, ventricular fibrillation or asystole)
- Serious EMD
- Serious cardiac rupture
- Serious acute ventricle septum defect

- Serious pericarditis
- Serious tamponade
- Serious sustained hypotension
- Serious recurrent myocardial ischemia
- Serious abrupt vessel closure
- Serious coronary spasm
- Serious coronary arterial dissection
- Serious hypersensitivity
- Serious anaphylactoid reaction
- Serious thrombocytopenia
- Drop of hemoglobin > 5 g/L
- PCI planned (after study PCI)
- CABG planned (after study catheterization / study PCI)

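### The SAP's rehospitalisation endpoints do not exclude scheduled readmissions, so a planned staged PCI would count as an event in the non-cardiac row.

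*SAP*

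**What the plan says.** **Collection.** Protocol 6.2.3.1 asks at day 30 for "Data on any rehospitalisation occurring after hospital discharge up to (including) day 30". Appendix B2 says that if a patient "is readmitted to the hospital until day 30 due to cardiac reasons, this information must be recorded in the eCRF", and its non-cardiac entry likewise collects any such readmission.

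**Role of scheduled.** For cardiac readmissions Appendix B2 reads: "Only if readmission was scheduled, e.g. because of a routine or planned procedure, will the event leading to rehospitalisation not be considered" an SAE. The non-cardiac entry has the same carve-out. In both, only SAE status is removed; the readmission is still collected.

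**Endpoints.** SAP 6.2 lists rehospitalisation for cardiac reasons and "Rehospitalization for non-cardiac reasons" at day 30, and SAP 6.5.2 lists both at 1 year. SAP 8.6 (relative risk, by the method of 8.5.1) and 8.9.2 (competing risks) analyse them. None of these sections restricts them to unscheduled readmissions.

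**Coding.** SAP 8.6 assigns reinfarction and CHF to cardiac, and stroke/ICH and a residual category to non-cardiac.

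**PCI text.** For PPCI, Protocol 4.1.4.2 states that "PCI of non-infarct related vessels is NOT recommended". The PhI text (4.1.4.1, 6.2.2.1) has no matching sentence and allows elective PCI where indicated at the planned catheterisation.

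**The concern.** A readmission arranged in advance to treat a second vessel is part of the treatment plan, not a failure of the reperfusion strategy. Scoring it as an efficacy event causes two separate problems.

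First, it adds events that carry no information about how well either strategy worked, which pulls the relative risk towards 1 even when both arms stage equally often.

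Second, if one arm stages after discharge more often than the other, the relative risk partly reflects when the second vessel was treated. The arm-specific PCI wording makes such a difference possible.

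The label would mislead as well: a coronary procedure would appear as a non-cardiac readmission in a trial whose open-label results are meant to generate hypotheses.

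**Working it through.** **Step 1: does a scheduled readmission count?** Protocol 6.2.3.1 and Appendix B2 collect all readmissions to day 30. The scheduled clause acts only on SAE status. SAP 6.2, 6.5.2, 8.6 and 8.9.2 contain no exclusion. The SAP does not say outright that scheduled readmissions count, but nothing in it would let a programmer leave them out.

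**Step 2: which row receives it?** Under SAP 8.6 a staged PCI is not reinfarction, CHF or stroke/ICH. It falls in the residual category and so in the non-cardiac row. It reaches the cardiac row only if a site records it under reinfarction or CHF.

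**Step 3: what about 1 year?** Protocol 5.3.2 collects only cardiovascular readmissions for days 31 to 365, with dates and primary reasons and no scheduled flag. SAP 6.5.2 nevertheless lists non-cardiac readmission at 1 year, and 8.9.2 gives no coding rule of its own. If the 8.6 coding carries over, the non-cardiac row in that period could hold only cardiovascular readmissions other than reinfarction and CHF, which is where a staged PCI would sit. The SAP history adds that completion of a later planned PCI is not recorded.

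**Step 4: illustration of size.** There is no plan figure to reproduce: the documents give no rehospitalisation rate, and the sample size is not derived from power. From Protocol 7.5: "Approximately 600 patients are planned to be randomized with 400 receiving PhI therapy and 200 PPCI". All rates below are assumptions. Let *b* be the risk of an unscheduled readmission in the affected row and *s* an independent risk of a staged readmission:

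observed risk = 1 − (1 − *b*)(1 − *s*)

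*Dilution, equal staging.* Take *b* = 5.0% PPCI and 3.5% PhI, so the true RR is 0.70, with *s* = 5% in both arms.
- PPCI: 1 − 0.95 × 0.95 = 9.75%
- PhI: 1 − 0.965 × 0.95 = 8.33%
- RR = 8.33 / 9.75 = 0.85
- Risk difference: 1.43 points, against a true 1.50

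The relative risk is therefore diluted much more than the risk difference.

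*Bias, unequal staging.* Take *b* = 5% in both arms, so the true RR is 1.00. The last column is the chance of two-sided p < 0.05 by the pooled two-proportion normal approximation with 400 and 200 patients.

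| Staged PPCI | Staged PhI | Observed PPCI | Observed PhI | RR (PhI/PPCI) | Chance p < 0.05 |
|---|---|---|---|---|---|
| 5% | 5% | 9.75% | 9.75% | 1.00 | 5% |
| 5% | 2% | 9.75% | 6.9% | 0.71 | 24% |
| 10% | 5% | 14.5% | 9.75% | 0.67 | 41% |
| 2% | 5% | 6.9% | 9.75% | 1.41 | 20% |

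With *b* from 3% to 8%, rows two and three span RR 0.62 to 0.78 and a 19% to 48% chance of p < 0.05. The last row shows the reverse case, since the documents do not fix the direction. Staging within the index stay sets *s* to zero and removes both effects.

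**The case against.** The strongest reply is that the difference between arms is inferred from silence. The PPCI sentence is a recommendation, not a ban. The PhI text does not name non-infarct vessels at all, and the protocol nowhere mentions staged PCI after discharge. SAP 6.6 lists later planned PCI for both arms alike. This stands. A reader might infer that PPCI will show excess readmissions and that the bias favours PhI; the documents do not establish either.

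A reader might also infer that both rehospitalisation rows, or an overall readmission RR, are distorted. The SAP has no all-readmission endpoint, and its coding rule largely shields the cardiac row.

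It can be added that SAP Tables 7.1 and 15.1 already show non-culprit PCI and later planned PCI by arm. That helps partly: one describes the study procedure and the other only an intention, so neither shows how many readmissions were staged procedures.

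Finally, Protocol 7.5 says "No primary hypothesis or primary endpoint have been formulated", and rehospitalisation comes last among the day-30 events that SAP 6.2 ranks by medical importance. That limits the consequence. It does not make a planned procedure an adverse outcome.

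**Conclusion.** The definition gap is real: as written, a planned staged PCI after discharge would be scored as an event in the non-cardiac rehospitalisation row at day 30, and at 1 year if the same coding is used. The cardiac row is largely unaffected.

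Dilution of the relative risk follows whenever staged readmissions occur. Bias between arms is a possibility that depends on unequal staging after discharge, and neither its presence nor its direction is shown. Every size given here rests on assumed rates.

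The endpoint is a low-ranked secondary one in an exploratory trial, so this is a correction to definition and reporting. It does not touch the composite of primary interest. It takes no position on which PCI rule is right.

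**What to change.** - **Day 30 (SAP 6.2, 8.6):** define both rehospitalisation endpoints as at least one unscheduled readmission. Derive the flag from SAE status in the eCRF, because Appendix B2 makes unscheduled readmissions SAEs. Use the eCRF record and not the expedited SAE form, which Protocol 5.2.1 does not require for unrelated events on the STEMI list.
- **Reporting:** show scheduled readmissions by arm in a separate descriptive row, so that planned procedures are not counted as non-cardiac events.
- **Days 31 to 365 (SAP 6.5.2, 8.9.2):** classify scheduled versus unscheduled from the recorded primary reasons, blinded to arm, where the data allow. State the limitation where they do not. State the coding rule used, and reconcile the 1-year non-cardiac row with Protocol 5.3.2, which collects only cardiovascular readmissions in that period.

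Cost: revised SAP wording, one derived flag at day 30 and a small review of reasons. There will be slightly fewer events, and classification after day 30 will remain incomplete.
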